3. STUDY OBJECTIVES AND ENDPOINTS

■ Purpose of the Study

The purpose of the study is to collect representative clinical images with demonstrated diagnostic image quality using ZTE MRAC and Q Static (Q. MRAC) software features. The images and summary data from this study are intended for use in regulatory submission(s).

■ Primary Objective:

To demonstrate diagnostic image quality of image sets with ZTE MRAC and Q Static (Q. MRAC) for SIGNA PET/MR in representative clinical cases of the general imaging population.

■ Secondary Objective(s):

To verify diagnostic acceptability, ease of use, and functionality of ZTE MRAC and Q Static (Q. MRAC) for SIGNA PET/MR at clinical sites.

■ Safety Objective(s):

To collect information about safety events and device issues.

■ Study Endpoints

■ Primary Endpoints:

Independent radiologist/nuclear medicine physician determination of diagnostic image quality considering all evaluable images from each subject (scored on a 5-pt Likert scale)

■ Secondary Endpoints:

Site level determination of diagnostic acceptability (Y/N) based on consensus between radiologist(s) and nuclear medicine physician(s) at the site

Ease of use per procedure rated on a 5-pt Likert scale score

Functionality rated for each feature per procedure on a binary (Y/N) performance scale

■ Safety Endpoints

Type and number of safety events (AEs and SAEs) and device issues (malfunctions, user errors, and labeling issues) will be summarized.

■ Summary of Study Design

This is a pre-market, open label, prospective, non-randomized clinical research study at one site. The study is designed to allow for sample PET/MR image collection and to demonstrate diagnostic image quality of resultant sample image sets from each participating subject. The results of this study will be analyzed according to a prospective Blinded Image Evaluation (BIE) plan and Statistical Analysis Plan (SAP) prepared by the Sponsor prior to the start of image reads. This study is run concurrently with other studies of the device conducted by the Sponsor and it is prospectively expected that the cumulative results of these studies may be used to support regulatory submissions.

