4. STUDY DESIGN

Study Population

Subjects will be enrolled that have a clinical indication for PET/CT or PET/MR with radiotracer injection prescribed for their medical care outside of the study. Sites should make reasonable attempts to ensure diversity of clinical state (including injury severity or extent of disease progression) within the enrolled population in order to achieve a sample maximally representative of the intended use population.

Number of Subjects

The study aims to acquire up to 75 clinical PET/MR image sets (up to 38 subjects will be enrolled to have a ZTE MRAC exam and the remaining 37 subjects will be enrolled to have a Q Static (Q. MRAC) exam. In the event that a subject scan does not produce images, as in the case of withdrawal or technical issues preventing scanning, additional subjects may be enrolled until the target number is achieved (not to exceed a maximum of 75 subjects during the course of the study) as described in [Section 10.2 - Sample Size Determination](#). The minimum number of necessary subjects will be enrolled to achieve the target number of datasets.

Enrollment Quota

Subjects will be enrolled based on a quota block method based on scan type (relative to the patient clinical indication for PET/CT or PET/MR). Each subject may have only one type of scan towards these quota blocks (ZTE or Q.Static MRAC), not both (Table 1).

Table 1. Target quota blocks for subject enrollment/target datasets

Scan Type	Target number of subject datasets ($N_{\text{Target}} = 30$)
ZTE MRAC	At least 30 subject scans ($N_{\text{neuro}} = 30$ to 38)
Q Static (Q. MRAC)	At least 30 subject scans ($N_{\text{body}} = 30$ to 37)

Protection of Vulnerable Subjects

Vulnerable subjects are individuals whose willingness to volunteer in a clinical investigation could be unduly influenced by the expectation, whether justified or not, of benefits associated with participation or of retaliatory response from senior members of a hierarchy in case of refusal to participate. The Sponsor shall avoid improper influence on, or inducement of, the subject, monitor, any investigator(s), or other parties participating in, or contributing to, the clinical investigation.

All investigators shall avoid improper influence on, or inducement of, the subject, Sponsor, monitor, other investigator(s), or other parties participating in, or contributing to, the clinical investigation.

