6. STUDY DATA COLLECTION AND ASSESSMENTS

Primary Assessment

Independent Reader Determination of Diagnostic Image Quality

Diagnostic image quality will be rated on a 5-pt Likert scale by at least 2 independent board certified nuclear medicine physician and/or radiologists for all evaluable image sets (including all clinically acquired MR image sets able to be successfully post-processed that are complete image sets [not from cases of withdrawal or critical deviation that could impair to the quality of data]). Independent reads will be conducted outside of the clinical care environment according to the procedures specified in the Blinded Image Evaluation (BIE) plan prepared by the Sponsor prior to the start of image reading. Identifiable subject information will be removed prior to independent reads.

Diagnostic image quality will be recorded on a 5-pt Likert scale, where ratings of ≥ 3 are considered acceptable for diagnostic use and ratings of 1-2 are considered unacceptable for diagnostic use, as follows:

1. **Unacceptable** (cannot be used for diagnostic use)
2. **Poor** (not completely suitable for diagnostic use)
3. **Acceptable** (suitable for diagnostic use but with minor defects)
4. **Good** (good suitability for diagnostic use)
5. **Excellent** (excellent suitability for diagnostic use)

The reader should record the rationale for any image scored unacceptable for diagnostic use (scores of 1 or 2). And/or provide comments in image annotation or point to the problem area in the images. Scores should be based on the entire image set, considering all available views, with the exception of the LAVA sequence used for MR-attenuation correction (which should not be considered in the evaluation for image quality).

Secondary Assessments

Site Determination of Diagnostic Acceptability

Based on consensus of at least one radiologist and at least one nuclear medicine physician at the site, diagnostic acceptability of each evaluable image set (including all clinically acquired MR image sets able to be successfully post-processed that are complete image sets [not from cases of withdrawal or critical deviation that could impair to the quality of data]).

Binary diagnostic image quality will be recorded by the site on a single CRF that includes the names and signatures of both the radiologist and nuclear medicine physician making the evaluation, as follows:

"Is the image of acceptable quality for diagnostic use? (Y/N)"

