There is always a chance of unexpected risks. Throughout the study, the Sponsor will evaluate and update safety information in study documents.

■ Adverse Event Definitions

Adverse Event (AE): any untoward medical occurrence, unintended disease or injury, or untoward clinical signs (including abnormal laboratory findings) in subjects, users or other persons, whether or not related to the investigational medical device [ISO 14155:2011 3.2]. This includes events related to the investigational device or the comparator and to the procedures involved. For users or other persons, this is restricted to events related to the investigational medical device.

Serious Adverse Event (SAE): an adverse event that led to death; led to a serious deterioration in the health of the subject, that either resulted in a life-threatening illness or injury, a permanent impairment of a body structure or a body function, or in-patient or prolonged hospitalization, or medical or surgical intervention to prevent life-threatening illness or injury or permanent impairment to body structure or a body function; or led to fetal distress, fetal death or a congenital abnormality or birth defect. Planned hospitalization for a pre-existing condition, or a procedure required by the protocol without serious deterioration in health, is not considered a SAE [ISO 14155:2011 3.37].

Adverse Device Effect (ADE): an adverse event related to the use of an investigational medical device [ISO 14155:2011 3.1]. This includes any adverse events resulting from insufficient or inadequate instructions for use, deployment, implantation, installation, or operation, or any malfunction of the investigational medical device. This includes any event that is a result of a user error or intentional misuse of the investigational device [ISO 14155:2011 3.43].

Serious Adverse Device Effect (SADE): an adverse device effect that has resulted in any of the consequences characteristic of a serious adverse event [ISO 14155:2011 3.36].

Device deficiency: an inadequacy of a medical device with respect to its identity, quality, durability, reliability, safety, or performance, such as malfunctions, use errors, and inadequate labelling [ISO 14155:2011 3.15].

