10. STATISTICAL METHODS

■ Statistical Hypothesis

No statistical hypothesis is being prospectively tested in this study. As necessary for regulatory submission, additional analyses will be detailed prior to the star to independent reads in the Statistical Analysis Plan (SAP) prepared by the Sponsor's biostatistician.

■ Sample Size Determination

The sample size is based on the Sponsor's engineering determinations of the required number of sample images, and is not prospectively powered to produce statistically powered results. The protocol aims to acquire 30 images using Q Static (Q. MRAC) and 30 images using ZTE. Datasets may include one or both image type, based on clinical availability, to meet these targets. Assuming that 10% of cases will include both types of data and 25% attrition rate due to various causes, this study requires a population (N) such as that:

$$1.1N - (1.10 \times N)(0.25) = 30 \text{ ZTE} + 30 \text{ Q static}$$

Study Title: Clinical Evaluation Of MP26 Features in Adults

Study No: 114.03-2016-GES-0001

To satisfy this requirement, a minimum population size of $N = 72$ is required. This is approximated to $N = 75$, as this number is considered by the Sponsor to be sufficient to account for unforeseen contributions to dropout or evaluable image rates.

■ Statistical Analysis

■ General Statistical Methods

The study data will be presented in tables, listings, and figures. Data will be summarized using descriptive statistics. The descriptive statistics for variables will include mean, standard deviation, median, Q1 and Q3, minimum, maximum, and count. Categorical variables will be described with counts, percentages. If necessary for regulatory submission, additional statistical methods may be employed as detailed in the Statistical Analysis Plan (SAP) prepared by the Sponsor's responsible biostatistician and stored in the study's clinical history file (CHF).

■ Analysis Set(s)

The study analysis sets include the Safety Population and Per-protocol population.

The safety population includes all subjects enrolled and scanned, the per-protocol population include all subjects enrolled, scanned, processed with ZTE and/or Q-static and without critical protocol deviation.

■ Analysis of Primary Endpoint(s)

General descriptive statistical methods will be used to summarize the study diagnostic image quality results by reader and overall.

■ Analysis of Secondary Endpoint(s)

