10.3 Interim Analysis

No interim analyses are prospectively planned as part of this study.

■ Handling of Missing Data

Analysis will be based on collected data, and no imputation will be done for missing data.

■ Deviation(s) from the Original Statistical Plan

Any changes or deviations from the original statistical plan specified in this protocol will be described and justified in the SAP and/or study final report as required by ISO 14155:2011.

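### Complete image sets that the investigational technology fails to post-process drop out of both image-quality endpoints, so any such failure makes the evaluable-only acceptable rate too favourable

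*Combined protocol and SAP*

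**What the plan says.** **Who is scored.** Section 3 defines the primary endpoint as a "determination of diagnostic image quality considering all evaluable images from each subject". Section 6, Primary Assessment, has this done "for all evaluable image sets (including all clinically acquired MR image sets able to be successfully post-processed that are complete image sets". The site's secondary assessment uses the same restriction: "diagnostic acceptability of each evaluable image set (including all clinically acquired MR image sets able to be successfully post-processed". Section 6 does not say what counts as successful processing.

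**Who is analysed.** In Section 10, Analysis Set(s), "the per-protocol population include all subjects enrolled, scanned, processed with ZTE and/or Q-static and without critical protocol deviation". Under Handling of Missing Data: "Analysis will be based on collected data, and no imputation will be done for missing data".

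**Where the processing happens.** The Synopsis (Procedures/Methods) and Section 5 (Activities after PET/MR Scanning) place it with the Sponsor or its delegate, using investigational software, after the images have left the site and before any read.

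**What else could record a failure.**
- The functionality items in Section 6 are answered by the device operator. They cover viewing images, positioning, and prescribing and scanning.
- Section 4 (Recruiting and Screening) and Section 5 (Activities after PET/MR Scanning) limit device issues to the time the subject is in the PET/MR suite.
- The safety endpoint in Section 3 and the Safety Assessments in Section 6 mention device issues with no time limit.
- Section 8 defines a device deficiency broadly, as "an inadequacy of a medical device with respect to its identity, quality, durability, reliability, safety, or performance".

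**The concern.** The step that decides whether a set may be scored uses part of what the study is testing. If the investigational technology cannot turn a complete acquisition into a readable set, that case leaves the denominator and is not counted against the technology. The remaining summary tells the reader how good the images are when processing works.

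That is a fair question, but the primary objective is wider: to demonstrate diagnostic image quality in representative clinical cases, with a regulatory submission in view. A reader of that submission could take the percentage acceptable among evaluable sets as the chance that a completed scan gives a diagnostic image. The two differ whenever a device-caused processing failure has occurred, and nothing in the protocol text requires such failures or their causes to be shown beside the result.

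**Working it through.** **Step 1. Follow one failed set through the protocol.** Take a complete PET and MR acquisition, without withdrawal or critical deviation, that the Sponsor's investigational processing cannot complete.

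- Independent score and site yes/no: excluded, because processing must have succeeded (Section 6).
- Per-protocol set: excluded, because the subject's data were not processed (Section 10).
- Imputation: none, so the set is not treated as unacceptable (Section 10).
- Functionality and ease of use: rated by the operator on the exam itself; no item asks about Sponsor processing (Section 6).
- Device issue: outside the window in Sections 4 and 5, which closes when the subject leaves the suite. Section 3 and the Safety Assessments in Section 6 could be read as including it, and the Section 8 definition would fit it. The text is inconsistent here.
- Safety set: the subject is included, but no image-quality endpoint is tied to that set.

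**Step 2. Inputs for the size.**

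- The plan states no processing failure rate and no yield per scan, so there is no figure of its own to reproduce on this point. Its only loss figure is 25% attrition from all causes (Section 10, Sample Size Determination), not split by cause.
- Acceptable means a score of at least 3, or a site answer of yes (Section 6). Reporting this as a percentage is inferred from that cut-off and from the use of percentages for categorical variables in Section 10; the protocol does not name an acceptable rate.
- E = 30 sets read per feature: an assumption, taken from the target of 30 images per feature.
- k = complete sets lost to processing failure caused by the investigational technology: not in the documents; an assumed range is shown.

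**Step 3. Formula.** With A acceptable sets, the evaluable-only rate is A/E. The rate with these failures counted as not acceptable is A/(E+k). The ratio of the first to the second is (E+k)/E = (30+k)/30, whatever the value of A above zero.

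**Step 4. Results** (exact Clopper-Pearson 95% intervals).

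| Acceptable among 30 read | k | Rate with failures counted | 95% CI | Overstatement |
|---|---|---|---|---|
| 30 | 0 | 30/30 = 100% | 88.4 to 100 | none |
| 30 | 1 | 30/31 = 96.8% | 83.3 to 99.9 | 3.2 points, factor 1.03 |
| 30 | 3 | 30/33 = 90.9% | 75.7 to 98.1 | 9.1 points, factor 1.10 |
| 27 | 0 | 27/30 = 90.0% | 73.5 to 97.9 | none |
| 27 | 1 | 27/31 = 87.1% | 70.2 to 96.4 | 2.9 points, factor 1.03 |
| 27 | 3 | 27/33 = 81.8% | 64.5 to 93.0 | 8.2 points, factor 1.10 |

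**Step 5. Outer limit.** Section 4 caps enrolment by feature: "up to 38 subjects will be enrolled to have a ZTE MRAC exam and the remaining 37 subjects will be enrolled" for Q.Static. If 30 sets are read, at most 38 − 30 = 8 ZTE and 37 − 30 = 7 Q.Static sets can be lost, for all reasons together. The factor cannot then exceed 38/30 = 1.27 or 37/30 = 1.23. Reaching it would need every loss to be a processing failure of investigational cause. It is a bound, not an expectation.

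**The case against.** **The endpoint is openly conditional and descriptive.** Section 3 says evaluable images, Section 10 tests no hypothesis, and the protocol promises no yield per scan. This stands: the evaluable-only summary is legitimate and should stay. What is missing is a companion result for failures of the technology itself.

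**Other documents may cover it.** Read procedures are left to the Blinded Image Evaluation plan and analyses to a separate SAP, both to be written before reads. Neither was available. This stands, and the point is confined to the protocol text.

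**Losses would be partly visible.** The safety set less the per-protocol set, allowing for listed critical deviations, gives an approximate count of unprocessed subjects. This stands for the count. It does not give the cause.

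**The shifts are small against sampling error.** For k = 1 or 3, the lower rate lies inside the interval around the evaluable-only rate. True, but that interval describes chance variation; it does not describe or correct a one-sided exclusion.

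**Stronger readings a reader might infer, and why they fail.**
- That replacement hides the failures. Section 4 says "additional subjects may be enrolled until the target number is achieved", but for scans that produce no images, with withdrawal and technical obstacles to scanning as its examples. A set that fails later in processing did produce images, so this rule does not clearly apply.
- That most sets missing between scanning and reading are processing failures. The documents give no breakdown, and critical deviations also enter that gap.
- That acquisition failures go unrecorded too. Section 5 requires a reason when PET and MR are not both collected, and the functionality items cover scanning.
- That the protocol plainly forbids recording processing failures as device issues. Its sections conflict on this.

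**Conclusion.** The concern holds as a conditional one. Under the rules in Sections 6 and 10, a complete set lost because the investigational technology failed to process it is dropped, not counted against the technology. If such losses occur, the percentage acceptable among evaluable sets overstates how often a completed scan yields a diagnostic image, by (30+k)/30 with 30 sets read: 1.03 for one failure, 1.10 for three, nothing for none.

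This rests on four assumptions: 30 sets read per feature, the values of k, the acceptable rate being the summary of interest, and the cause lying with the investigational technology. A failure with a documented non-device cause says nothing against the device. No test or error rate is affected. Severity is minor to moderate, and the point falls away to the extent that the separate SAP or reading plan already handles it.

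**What to change.** Keep the evaluable-only summary as planned. In the SAP, the reading plan or a protocol amendment, before reads start:

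1. State what counts as successful post-processing, and log each failure with its cause. Assign the cause blind to scores.
2. Reconcile the device-issue window in Sections 4 and 5 with Section 3, the Safety Assessments in Section 6 and the Section 8 definition, so that a processing failure caused by the investigational technology is recorded as a device issue whenever it occurs.
3. Report by feature the numbers scanned, sent for processing, failed by cause, and read.
4. Add one supplementary acceptable rate per feature, separately for each reader (score at least 3) and for the site (yes). The denominator is sets read plus complete sets lost to post-processing failure attributed to the investigational technology, with the latter counted as not acceptable.
5. Show failures of undetermined cause as a sensitivity bound, by also counting them as not acceptable. Withdrawals, critical deviations, acquisition failures and failures with a documented non-device cause stay out of this denominator, so it should not be labelled a yield per subject scanned.

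The cost is wording, one log field and one table, with no extra scans or reads. The supplementary rate may come out lower than the evaluable-only rate.

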7. QUALIFICATION AND TRAINING PLAN

■ Staff Qualifications

All members of the study staff participating in the conduct of the investigation shall be qualified by education, training and/or experience to perform their tasks, and this shall be documented appropriately, as per US FDA and ISO 14155:2011.

■ Reader Qualifications

All readers in this study will:

- Have >4 years of direct experience in evaluating MRI and/or PET image sets.
- Be certified as diagnostic radiology and/or nuclear medicine physicians.

■ Training Plan for the Protocol and Research Device/Product

Before starting the study, the study staff will be trained on the clinical investigation requirements set forth in this study protocol according to the study *Training Plan* stored in the Sponsor's Clinical History File (CHF).

Study staff directly operating or maintaining the investigational PET/MR system will be trained based on the training plan and device documentation. Device operators will be qualified to operate the devices, as per the policies of the site.

The Principal Investigator will be ultimately responsible for execution of this study in accordance with the protocol and for devices used in this study by members of the study staff.

8. SAFETY

■ Anticipated Adverse Events

MR technologies up to 3.0T have been used in clinical applications for over 30 years and have a well-documented safety profile. Similarly, PET scanners are widely used in clinical practice. The PET/MR scanner does not involve any risks other than those normally associated with routine clinical PET and MRI scans, similar to those already performed in many hospitals. The following are some discomfort one may experience during a PET/MR scan session.

Movement of metal objects: PET/MR systems operate in a high field magnetic field typical of MRI systems, which can cause movement or projectile motion of certain ferrous metal objects. Though injuries are rare (occurring in less than one of 100,000 patients), small objects can cause bruises or cuts, and large objects can cause severe trauma or even death.

Implants: Objects embedded within the body can be affected by the strong external magnetic field near and inside of the PET/MR device during an MRI exam, causing movement and/or electronic malfunction that can lead to injury or even death.

Warming and burns: Radiofrequency (RF) energy transmitted by the PET/MR system during MRI scanning can result in generalized or localized heating of body tissues, occurring in about 5-10% of

patients. Some subjects may experience sensations of warming and/or perspiration, which can be uncomfortable. Though warming can cause burns, severe injuries are rare.

Peripheral nerve stimulation (PNS): During a PET/MR exam, rapidly changing magnetic fields during MRI exams can cause stimulation of nerves, causing unusual generalized or localized “tingling” sensations, known as peripheral nerve stimulation (PNS). PNS normally occurs in 5-10% of subjects, but may occur in up to 50% of subjects under certain conditions.

Acoustic Noise: During PET/MR, the MRI system is capable of generating acoustic noise levels higher than 99dB. The acoustic noise levels of the system do not exceed 140 dB under worst-case conditions. Sometimes, transient hearing loss or “ringing” in the ears (tinnitus) can occur, which it typically is mild and resolves spontaneously after scanning. Severe or chronic hearing conditions can occur if proper hearing protection is not used, but are rare (occurring in less than one of in 100,000 patients).

PET Radiotracers and MR contrast agents: Subjects in this study will be administered PET radiotracers prescribed as part of their normal medical care, and dosage will not be changed or increased by participating in this study. Though no MR contrast agents are being administered solely for the purposes of this study, some patients may have incidentally received MR contrast as part of regular medical care prior to starting study procedures. The safety and risk profiles of PET radiotracers and MR contrast agents are well documented and are not increased by having a PET/MR scanning. These risks vary by the type of agent administered, but most commonly include:

- warm or hot (“flushed”) sensations that typically resolve spontaneously;
- transient “metallic” taste that typically resolves spontaneously;
- allergic reactions, ranging from mild irritation, such as itching and hives that may resolve spontaneously, to a life-threatening emergency (anaphylactic reaction) that requires additional medical care;
- kidney damage as the agent is excreted from the body, a potentially severe condition called nephrotoxicity. Risk is increased for subjects with diabetes, chronic renal disease, advanced congestive heart failure, concomitant use of non-steroidal anti-inflammatory agents (NSAID).
- unintentional penetration of agents into the local areas surrounding tissues, either by leakage (e.g., because of brittle veins in very elderly patients) or direct exposure (e.g. because the needle has punctured the vein and the infusion goes directly into the arm tissue), a condition known as extravasation. Extravasation typically causes mild effects, such as pain, reddening, or irritation at the injection site, but can, in rare cases, cause severe injury requiring medical care.
- for PET radiotracers, a radioactive drug (radiotracer) is injected into the body. This results in a small amount of radiation exposure, at very low levels not typically associated with any adverse effects on the body.
- for gadolinium-based MR contrast agents, a rare and serious side effect of contrast administration is formation of fibrotic nodules and indurations on the skin and other tissues throughout the body, called nephrogenic systemic fibrosis (NSF), which is painful and typically requires additional medical care.

Due to possible effects in the developing fetus and health of the mother, no women that are pregnant or suspected to be pregnant will be included in this study.

There is always a chance of unexpected risks. Throughout the study, the Sponsor will evaluate and update safety information in study documents.

■ Adverse Event Definitions

Adverse Event (AE): any untoward medical occurrence, unintended disease or injury, or untoward clinical signs (including abnormal laboratory findings) in subjects, users or other persons, whether or not related to the investigational medical device [ISO 14155:2011 3.2]. This includes events related to the investigational device or the comparator and to the procedures involved. For users or other persons, this is restricted to events related to the investigational medical device.

Serious Adverse Event (SAE): an adverse event that led to death; led to a serious deterioration in the health of the subject, that either resulted in a life-threatening illness or injury, a permanent impairment of a body structure or a body function, or in-patient or prolonged hospitalization, or medical or surgical intervention to prevent life-threatening illness or injury or permanent impairment to body structure or a body function; or led to fetal distress, fetal death or a congenital abnormality or birth defect. Planned hospitalization for a pre-existing condition, or a procedure required by the protocol without serious deterioration in health, is not considered a SAE [ISO 14155:2011 3.37].

Adverse Device Effect (ADE): an adverse event related to the use of an investigational medical device [ISO 14155:2011 3.1]. This includes any adverse events resulting from insufficient or inadequate instructions for use, deployment, implantation, installation, or operation, or any malfunction of the investigational medical device. This includes any event that is a result of a user error or intentional misuse of the investigational device [ISO 14155:2011 3.43].

Serious Adverse Device Effect (SADE): an adverse device effect that has resulted in any of the consequences characteristic of a serious adverse event [ISO 14155:2011 3.36].

Device deficiency: an inadequacy of a medical device with respect to its identity, quality, durability, reliability, safety, or performance, such as malfunctions, use errors, and inadequate labelling [ISO 14155:2011 3.15].

Unanticipated serious adverse device effect (USADE): a serious adverse device effect, which by its nature, incidence, severity, or outcome has not been identified in the current version of the risk analysis report [ISO 14155:2011 3.42]. In the United States, any serious adverse effect on health or safety or any life-threatening problem or death caused by, or associated with, a device, if that effect, problem, or death was not previously identified in nature, severity, or degree of incidence in the study documents, will be reported in accordance with 21 CFR §812.3 and applicable laws and regulations.

■ Documentation of Safety Events

All adverse events (AE), including all serious adverse events (SAE), are required to be collected, investigated, and documented during the study reporting period, as defined in the study procedure as the time the subject enters until the time the subject leaves the PET/MR suite. Documentation will include:

- Description of Event

- Date of onset and resolution
- Severity (mild, moderate, or severe)
 - *Mild*: Symptom(s) barely noticeable to the subject or does not make the subject uncomfortable. The AE does not influence performance or functioning. Prescription drugs are not ordinarily needed for relief of symptom(s).
 - *Moderate*: Symptom(s) of a sufficient severity to make the subject uncomfortable. Performance of daily activities is influenced. Treatment of symptom(s) may be needed.
 - *Severe*: Symptom(s) of a sufficient severity to cause the subject severe discomfort. Treatment for symptom(s) may be given.
- Serious (yes/no)
- Causal relationship to investigational medical device? (not related, possibly related, or related)
 - *Not related*: The adverse event is reasonably expected to be related to (or caused by) a concurrent illness, effect of another device/drug or other cause, and is unlikely related to the investigational product.
 - *Possibly related*: The adverse event is reasonably expected to be related to the investigational product, and an alternative etiology is equally or less likely compared to the potential relationship to investigational product.
 - *Related*: There is a strong relationship to investigational product or recurs on re-challenge, and another etiology is unlikely or there is no other reasonable medical explanation for the event.
- Treatment given and/or action taken (procedure stopped, withdrawn from study, or no action)
- Anticipated (yes/no): Anticipated adverse events for this study are defined in Section Anticipated Adverse Events.

■ Reporting of Safety Events and Device Deficiencies/Complaints

The following events are to be reported to the Sponsor within 72 hours of the event occurrence and to the EC per their policy:

- All SAEs and USADEs
- All device issues that could possible lead to an SAE

Any study-related death should be reported to the Sponsor with 24 hours. Additional follow-up information may be requested by the Sponsor. In addition, safety information may be shared with regulatory agencies and other participating sites, as required by applicable law and regulation.

■ Device Deficiencies/Complaints

Device deficiencies/complaints should be reported to the study Sponsor contact identified on the cover page of this protocol. All device deficiencies/complaints will to be collected, fully investigated, and documented in the source document and appropriate case report form (CRF) during the study reporting period. The Principal Investigator is responsible for notifying the Sponsor in the event that there is any device issue that could potentially lead to a SAE.

